Issue subject diaries n		2,	х		x	х		x	х	х	x				
Collect subject diaries		38 8		x	x	х	x	2	х	x	х	x			
Record AEs since last visit	x	x	x	x	x	x	x	x	x	x	x	x	x	x	x
Local reaction assessment o			х	x	x	x	x	x	x	x	x	х			
Record concomitant medications/ products/ vaccinations		x	x	x	x	x	x	x	x	x	x	x	₹ X	x	x
Ask about the health condition of subject	x	x	x	x	x	x	x	x	х	x	х	x	x	x	x

a Demographic information, to be obtained at Screening Visit, will include age (date of birth), sex, race, and ethnicity as provided by the subject.

Medical history (incl. alcohol intake) will be collected at Screening Visit and at Visit 1 (Day 1) and will include any medical history that may be relevant to subject eligibility for trial participation such as prior vaccinations, concomitant medications, and previous and ongoing illnesses or injuries. Relevant medical history can also include any medical history that contributes to the understanding of an AE that occurs during trial participation, if it represents an exacerbation of an underlying disease/preexisting problem. Adverse occurrences before the prime vaccination of investigational vaccine/placebo are considered medical history.

<sup>c Complete physical examination (including height and weight) will be performed at Screening Visit. All subsequent are brief (symptom-directed) physical examinations, performed if deemed necessary or indicated by review of the subject's medical history, should assess clinically significant changes from the baseline examination. The findings

- should be documented in the subject's source document and transcribed into the electronic Case Report Form (eCRF). For any procedures at the site, the investigator shall follow his/her standard practice.
- d Vital signs will be performed at each on site visit, and at 1, 3, and 6 h (±15 min) post each immunization. Vital signs include systolic/diastolic blood pressure, pulse rate, respiratory rate, and body temperature.
- e In WOCBP women only: collect blood sample for testing β-hCG.
- f Urine analysis: glucose, bilirubin, ketone, specific gravity, blood, pH, protein, urobilinogen, nitrite, and leukocytes. Microscopic urinalysis (based on dipstick results): urine sediment will be microscopically examined for the presence of red blood cells, white blood cells, casts, crystals, epithelial cells, and bacteria.

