- g Clinical laboratory: (Chemistry) alkaline phosphatase, creatinine, ferritin, C-reactive protein, albumin, alanine aminotransferase, amylase, aspartate aminotransferase, gamma glutamyl transpeptidase, total bilirubin, blood urea, fasting blood sugar, lipase, sodium, potassium, calcium; (Hematology) hemoglobin, hematocrit, red blood cell count, white blood cell count and differential (neutrophils, lymphocytes, monocytes, eosinophils, basophils), platelet count.
- h Clinical laboratory tests (thyroid function): triiodothyronine (T3), thyroxine (T4), thyroid stimulating hormone.
- i Clinical laboratory tests (coagulation function): prothrombin time (PT), activated partial thromboplastin time (APTT), thrombin time (TT)), fibrinogen (FIB).
- j SARS-CoV-2 testing, including RT-PCR test of nasopharyngeal swabs and SARS-CoV-2 antibodies screening. See Appendix C for procedures of collecting and handling specimens of nasopharyngeal swabs.
- k Eligible virus naïve subjects with normal chest CT image enrolled at Screening will enter each cohortwill be randomized to vaccination of BNT162b1 or placebo at Visit 1, within 7 days after Screening Visit 0.
- Each randomized subject will receive two doses of either BNT162b1 (10 or 30 μg) or placebo intramuscularly (IM) one vaccination each at Visit 1 (on Day 1) and at Visit 5 (on Day 22), conduct injections at one third of the deltoid muscle (preferably in the non-dominant arm).
- n Each subject will receive diary cards to collect solicited reactions for 14 days after each vaccination (including the days of vaccine/placebo vaccination), and unsolicited AEs for 21 days after prime vaccination and 28 days after boost (including the days of vaccine/placebo vaccination).
- o From the beginning of prime vaccination to 28 days after boost, local reaction assessment should be conducted at 1, 3 and 6 h (±15 min) after each vaccination and at each site visit after vaccination.

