## 4.2.4.1 Safety summary

According to the periodic summary of the United States Phase I/II clinical study, pain at the injection site was the most common local reaction within 7 days of the first dose and the second

dose of vaccine; after the first vaccination, probability of pain in 10  $\mu g$  group was 58.3% (7/12), in 30  $\mu g$  group and 100  $\mu g$  group were 100.0% (12/12), and in placebo group was 22.2% (2/9). After the second vaccination, there were 83.3% and 100.0% of subjects got pain respectively in the dose level of 10  $\mu g$  and 30  $\mu g$ , while 16.7% subjects in placebo group got pain. All local reactions were mild or moderate except the 100  $\mu g$  group reported severe pain after inoculation of BNT162b1.

Within 7 days of each vaccination, the most common systemic events reported in BNT162b1 and placebo groups were mild to moderate fatigue and headache. Fatigue and headache were more common in BNT162b1 than that in placebo group. Furthermore, chills, muscle pain and joint pain were reported in the BNT162b1 group, but not in the placebo group. Systemic events increased with dose levels, and there were an increased number of subjects reporting systemic events after the second vaccination (10  $\mu$ g and 30  $\mu$ g groups). After the first vaccination, there were 8.3% (1/12) of subjects respectively in 10  $\mu$ g group and 30  $\mu$ g group, and 50.0% (6/12) of subjects in 100  $\mu$ g group got fever (defined as  $\geq$ 38.0° C). Based on the reactogenicity reported after the first dose of 100  $\mu$ g and the second dose of 30  $\mu$ g, subjects initially received 100  $\mu$ g of vaccination will no longer receive the second vaccination. After the second vaccination, 8.3% (1/12) of subjects in 10  $\mu$ g group and 75.0% (9/12) of subjects in 30  $\mu$ g group got fever  $\geq$ 38.0° C. The fever usually got resolved within 1 day of onset. There was no systemic event or fever of grade 4. Most local reactions and systemic events peaked 2 days after vaccination and resolved at day 7.

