# Please note:

Diary cards will be the only source document allowed for remote collection of solicited local and systemic reactions (including body temperature measurements). The following additional rules apply to the documentation of safety information collected by diary card:

- o Diary cards should be reviewed with the subject.
- No corrections or additions to the diary card will be allowed after it is reviewed with the investigator/designee.
- O Any data that are identified as implausible or incorrect, and confirmed by the subject to be a recording error should be corrected by the subject on the diary card (the correction should include a single strikethrough line and should be primeed and dated by the subject).
- Any blank or illegible fields on the diary card not otherwise corrected as above will be missing in the eCRF.
- The study site should enter all readable entries on the diary card into the eCRF.
- O Any newly described solicited safety information should be added to the diary card by the subject and primeed and dated. Any new unsolicited safety information would be recorded in the subject source document as a verbally reported event and therefore captured as an AE and recorded in the AE eCRF.
- Starting on the day of vaccine/placebo administration, the subject will check for specific types of events at the vaccination site (solicited local reactions), any specific generalized symptoms (solicited systemic reactions), body temperature (axillary), any other symptoms or change in the subject's health status, and any medications taken. These solicited reactions and body temperature will be recorded in the diary. Assessments should preferably take place in the evening at day's end using the same method of measurement every day.
- Temperature measurement is to be performed using the thermometer provided by the study site. If the subject feels unusually hot or cold during the day, the subject should

- check his/her temperature. The highest body temperature measured that day should be recorded on the diary card.
- The measurement of solicited local reactions (pain/tenderness, erythema/redness, and induration/swelling) is to be performed using the ruler provided by the study site. If multiple measurements are taken during the day, the highest measured value should be recorded on the diary card.

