- O The collection on the diary card of body temperature, solicited local reactions, and solicited systemic reactions will continue for a total of 14 days following each vaccine/placebo administration. The collection on the diary card of unsolicited AEs and medications will continue for 21 days following prime vaccination and 28 days following boost vaccination.
- The healthcare professional reviewing the data on the diary cards will discuss the AEs (if any) reported by the subject and will determine if any additional diagnoses and/or AEs are present and/or concomitant medications have been used.
- 3. At Visit 5 (Day 22), review the previous diary card with the subject and collect it.
- 4. Provide contraception guidance (see Section 9.1.8).
- 5. Provide the subject with a written reminder of the next planned trial activity. The subject will be reminded to complete the diary card daily and to contact the study site if there are any questions and to contact the site immediately (or as soon as the subject is medically stable) if the subject has a medical condition that leads to a hospitalization or an emergency room visit or is otherwise perceived as serious. Available contact details will be provided to the subjects.
- 6. Schedule the next site visit with the subjects.

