#### 9.3.5 Main visits post vaccination

The following main visits post vaccination will be performed:

- 1. Collect travel history (to SARS-CoV-2 endemic countries and SARS-CoV-2 endemic regions of China) and concomitant medications/vaccinations (see Section 9.1.2).
- 2. Perform symptom-directed physical examination (if deemed necessary, see Section 9.1.4).
- 3. Check vital signs (see Section 9.1.5).
- 4. Collect blood samples for routine safety laboratory testing, immunogenicity assessment and CMI testing (see Section 9.1.6).
- 5. Collect urine sample for routine safety laboratory testing (urinalysis; see Section 9.1.6).
- 6. Review the previous diary card with the subject and collect it (see Section 9.3.4).
- 7. Provide the subject with a new diary card, and remind the subject on how to use it (see Section 9.3.4).
- 8. Provide contraception guidance (see Section 9.1.8).

- 9. Provide the subject with a written reminder of the next planned trial activity. The subject will be reminded to complete the diary card daily. The subject will be reminded to contact the site if there are any questions and to contact the site immediately (or as soon as the subject is medically stable) if the subject has a medical condition that leads to a hospitalization or an emergency room visit or is otherwise perceived as serious. All contact details will be provided to the subject.
- 10. Schedule the next site visit with the subjects.

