7.1.1 General Analysis Method

Descriptive Statistics

Unless otherwise specified, the following descriptive statistics will be provided according to the type of variable:

- ✓ Continuous variables will be summarized by mean, standard deviation (SD), median, minimum (min) and maximum (max).
- ✓ Category or ordinal variables will be summarried by the number and percentage, where the percentage will be calculated based on the number of subjects in the corresponding analysis set as denominator and may be presented with exact 95% Clopper-Pearson CIs.

Additionally, descriptive statistics of titer and fold increase of titer will include geometric mean and its two-sided 95% confidence interval (CI). The geometric mean titer (GMT) is calculated as the mean of the logarithm of the functional antibody titers, back-transformed into the original scale. Two-sided CIs will be obtained by calculating CIs using Student's t-distribution for the mean of the logarithmically transformed assay results and transforming the limits back to the original scale.

Geometric mean fold rise (GMFR) is calculated as the mean of the difference of logarithmically transformed assay results (post vaccination time point – pre vaccination time point) and back-transformed into the original scale. Two-sided CIs will be obtained by calculating CIs using Student's t-distribution for the mean difference of the logarithmically transformed assay results and transforming the limits back to the original scale.

Decimal Places

Unless otherwise specified, the decimal places will follow the following rules:

- \checkmark The decimal places of min, max, median, Q1 and Q3 are consistent with the original data.
- ✓ The decimal places of mean, GM, SD and 95% CI are 1 more than the original data.
- ✓ Keep 2 decimal places in the percentage.

- ✓ Keep 2 decimal places in coefficient of variation (CV) and geometric coefficient of variation (GCV).
- ✓ Keep 4 decimal places if the p value is no less than 0.0001, and present as "<0.0001" if the p value is less than 0.0001.

- ✓ Keep 3 decimal places for all testing statistics.
- ✓ Keep 2 decimal places for the derived data.

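### Both Table 2 schedules collect the diary at Visit 2 (24 h after prime) without issuing a new one until Visit 3, against the 14-day recording rule; followed literally, this opens a gap over the expected reaction peak

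*Protocol*

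**What the plan says.** Table 2 of the Protocol has a schedule of activities for each age group. In both, the row "Issue subject diaries" is marked at Visit 1 (after prime), 3, 4, 5 (after boost), 6, 7 and 8. The row "Collect subject diaries" is marked at Visits 2, 3, 4, 5 (before boost), 6, 7, 8 and 9. Visit 2 is at 24 h (±2 h) and Visit 3 is on Day 8 (±1 day). Section 9.3 refers to Table 2 as the schedule for all trial procedures.

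The text around the table requires unbroken recording:
- Footnote n: "Each subject will receive diary cards to collect solicited reactions for 14 days after each vaccination".
- Section 9.3.4: diary collection of temperature and solicited reactions "will continue for a total of 14 days following each vaccine/placebo administration".
- Section 10.2.1: the window is the vaccination day and the 13 days after it.
- Section 9.3.5, after the step that collects the previous card: "Provide the subject with a new diary card, and remind the subject on how to use it". It lists no exception for Visit 2.

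Section 9.3.4 also states: "Diary cards will be the only source document allowed for remote collection of solicited local and systemic reactions". For timing, Section 4.2.4.1 reports from the US study: "Most local reactions and systemic events peaked 2 days after vaccination and resolved at day 7".

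**The concern.** Solicited local and systemic reactions over 14 days after each dose are the first two of the three primary endpoints (Section 5.2.1). Table 2 is what a site will work from visit by visit. Section 9.3.5 is a general list that names no visits and includes blood and urine sampling, which happens only at some of them, so staff must go to the table to see what applies when. At Visit 2 the table tells them to take the card and does not tell them to give another.

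The days at risk are the ones that matter most for reactogenicity, and they are at risk after the prime dose only. Solicited reactions are to be summarised separately for each immunization, so a loss confined to the prime would distort the prime-versus-boost comparison as well as the prime rates. The Safety Review Committee uses 14-day post-prime data, including diary events, to decide on the boost, and post-prime adult data to decide on opening the elderly group.

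**Working it through.** There is no stated figure to reproduce. The check is a count of marks and then of days.

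**1. Pair issues with collections (identical in both tables).**

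| Card issued | Next collection | Covered |
|---|---|---|
| Visit 1 (Day 1) | Visit 2 (24 h) | yes |
| none at Visit 2 | Visit 3 (Day 8) | no card issued |
| Visit 3 | Visit 4 (Day 15) | yes |
| Visit 4 | Visit 5, before boost (Day 22) | yes |
| Visit 5, after boost | Visit 6 (Day 29) | yes |
| Visit 6 | Visit 7 (Day 36) | yes |
| Visit 7 | Visit 8 (Day 43) | yes |
| Visit 8 | Visit 9 (Day 50) | yes |

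Issues: 7. Collections: 8. The only break is between Visits 2 and 3. After the boost there is no 24 h visit and every collection before Visit 9 comes with a new issue, so there is no gap.

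**2. Count the post-prime diary days without a card under a literal reading.**

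Inputs: Visit 3 on Day 7, 8 or 9 (Table 2). Entries are preferably made in the evening (Section 9.3.4), so with daytime vaccination, which is an assumption, the Day 2 entry would fall after the Visit 2 collection. The window is Days 1 to 14 (Section 10.2.1).

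Uncovered days = (day of Visit 3) − (first day without an entry).

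| Visit 3 on | Day 2 not entered (first = 2) | Day 2 entered before collection (first = 3) |
|---|---|---|
| Day 7 | 7 − 2 = 5 | 7 − 3 = 4 |
| Day 8 | 8 − 2 = 6 | 8 − 3 = 5 |
| Day 9 | 9 − 2 = 7 | 9 − 3 = 6 |

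Central case: 6 / 14 = 43% of diary days. Full range: 4 / 14 = 29% to 7 / 14 = 50%.

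**3. Locate the peak.** Vaccination is Day 1, so 2 days after vaccination is Day 3. Day 3 is uncovered in all six cases.

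**4. Follow the data into the analysis.** SAP 7.1.1 says that "the percentage will be calculated based on the number of subjects in the corresponding analysis set as denominator", and SAP 7.9 says missing data are not handled. A subject with a reaction that no one captured therefore stays in the denominator without counting in the numerator. The effect on the endpoint depends on how many subjects had a reaction only during the gap and had it missed by every other route. The documents give no figure for that, so no endpoint bias is calculated here.

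**The case against.** The strongest defence is that this is a missing mark, not a planned gap. Table 2 itself collects a card at Visit 3, which makes sense only if subjects hold one between Visits 2 and 3. Footnote n is attached to the issue row and requires 14 days of recording. Sections 9.3.4, 9.3.5 and 10.2.1 point the same way. Only one blank cell per table points the other way, and many sites would notice. This stands, and it fixes the nature of the finding: an internal contradiction with a risk attached.

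Nor are diaries the only route. Section 9.3.4 restricts remote collection to the diary, but Visits 2 and 3 also include on-site assessment of local reactions, vital signs with temperature, and recording of adverse events since the last visit. The committee sees vital signs, laboratory data and examination findings as well. This stands in part. Around Day 8 an on-site look can miss reactions that Section 4.2.4.1 describes as mostly resolved by day 7, and fever that usually cleared within 1 day. Questioning may recover events, but not the daily grades and temperatures.

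A reader might infer that reactions will go unrecorded in all 144 subjects, or that losing 43% of diary days means a 43% effect on the reaction rates. Neither is supported. The first assumes that every site follows the blank cell against the text. The second confuses days with occurrence: a subject counts as having a reaction if it is captured once in the window, for example on Day 1, at the 1, 3 or 6 h checks, at 24 h or from Visit 3 on. Section 9.3.4 also has blank diary fields entered as missing, so a lost day is not itself recorded as reaction-free.

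Text extraction is an unlikely explanation. Some cells carry stray characters and the original layout cannot be seen, but the same cell is blank in both tables.

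**Conclusion.** The inconsistency holds in both age groups: 8 collections against 7 issues, with no issue at Visit 2, in conflict with footnote n and Sections 9.3.4, 9.3.5 and 10.2.1.

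The consequence is conditional on a site following Table 2 literally. In that case about 6 of 14 post-prime diary days have no card (5 to 7 with evening entries; 4 to 6 if Day 2 is entered before collection), the expected Day 3 peak is always among them, and only the prime dose is affected. Post-prime rates of solicited reactions could then be understated relative to post-boost, with incomplete diary data reaching the Safety Review Committee. The direction of the bias follows from the SAP's denominator rule. Its size cannot be derived from the documents. The mark count and the contradiction are certain; how many sites or subjects would be affected is not known.

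**What to change.** Add a mark for "Issue subject diaries" at Visit 2 in schedules 1-1 and 2-1. Issues and collections then match at 8 and 8, and all 14 post-prime days are covered. State in Section 9.3.5 that any diary collected during the collection period is replaced at the same visit.

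Treating Visit 2 as a review after which the subject keeps the card would also close the count, but it is not a clean alternative: Section 9.3.4 bars corrections or additions once a card has been reviewed with the investigator or designee. That rule would have to be reconciled first.

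Cost: one table cell in each of two tables, one sentence of text, and one more card per subject at a visit that already takes place. No added visit or procedure, and no change to the SAP.

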# 1-2 Schedule of blood collection of adult subjects

Visit times	Visit 0	Visit 1 Before prime vaccination	Visit 1 Prime vaccination & after vaccination	Visit 2	Visit 3 7 days after prime vaccination	Visit 4 14 days after prime vaccination	Visit 5 Before boost vaccination	Visit 5 Boost vaccination & after vaccination	Visit 6 7 days after boost vaccination	Visit 7 14 days after boost vaccination	Visit 8 21 days after boost vaccination	Visit 9 28 days after boost vaccination	Visit 10	Visit 11	Visit 12
Time Points	Screening D -14~D 0	Day 1	Day 1	24 h (±2 h)	Day 8 (±1 d)	Day 15 (±1 d)	Day 22 (±2 d)	Day 22 (±2 d)	Day 29 (±3 d)	Day 36 (±3 d)	Day 43 (±4 d)	Day 50 (±4 d)	Month 3 (D 85 ±7d)	Month 6 (D 184 ±9d)	Month 12 (D 366 ±9d)
Blood routine (anticoagulant)	2 ml		17.65	2 ml	2 ml	(288 74)	2005	1202	2 ml	 2008	4	 2500	7.22		ULUEN
Blood chemistry (procoagulant)	4 ml	200	7777	4 ml	4 ml	1000	-	3 <del>944</del>	4 ml			-		1	Hereig
Ferritin (procoagulant)	4 ml	2777/23	777	4 ml	4 ml	25-72 A	577	-	4 ml	3 80 5050	2707	500	NUMB	755	FEET/2
Thyroid function (procoagulant)	3 ml	######################################	1555	3 ml	2200	(FEE)	State	1. III.	3 ml		H <del>ora</del> l	5555	Divis.	3 ml	5000
Coagulation function (anticoagulant)	2 ml	948.7%	2000	2 ml	18_234	1000	25,500	200	2 ml	5.00 500	1000	122			10.00
Pregnancy test (procoagulant)	3 ml	<del></del> 0	100	-		( <del>exe</del> )	3 ml	( <del>1-71-</del> 1)	( <del></del> )					( <del>)</del>	
IgG antibody (procoagulant)	1202	7.5 ml	17005	 		1 0100 1	7.5 ml	7000	7.5 ml	 2000	7.5 ml	7000	7.5 ml	7.5 ml	7.5 ml
Neutralizing antibody (procoagulant)	1222	7.5 ml	-	-		(200)	7.5 ml		7.5 ml	222	7.5 ml	ł	7.5 ml	7.5 ml	7.5 ml
ICS (anticoagulant)	12223	25 ml	100	-	NAME OF TAXABLE PARTY.	12023	1,000	TENEX.	25 ml	200	25 ml	544	1000	25 ml	1000
Total volume of blood collected	18 ml	48 ml	2222	15 ml	10 ml	12245	18 ml	2000	63 ml	2722	48 ml	- 1200	15 ml	51 ml	15 ml

Total volume of blood collected: 301 mL

# 2-1 Schedule of activities of elderly subjects

Procedure/Assessm ent	Visit 0	Visit 1 Before prime vaccination	Visit 1 Prime vaccination & after vaccination	Visit 2	Visit 3 7 days after prime vaccination	Visit 4 14 days after prime vaccination	Visit 5 Before boost vaccination	Visit 5 Boost vaccination & after vaccination	Visit 6 7 days after boost vaccination	Visit 7 14 days after boost vaccination	Visit 8 21 days after boost vaccination	Visit 9 28 days after boost vaccination	Visit 10	Visit 11	Visit 12
Time Points	Screening D -14~D 0	Day 1	Day 1	24 h (±2 h)	Day 8 (±1 d)	Day 15 (±1 d)	Day 22 (±2 d)	Day 22 (±2 d)	Day 29 (±3 d)	Day 36 (±3 d)	Day 43 (±4 d)	Day 50 (±4 d)	Month 3 (D 85 ±7d)	Month 6 (D 184 ±9d)	Month 12 (D 366 ±9d)
Informed consent	х														
Inclusion/exclusion criteria	x	x (review)												5	
Demographic data a	x														
Medical history (incl. alcohol intake) b	x	x (update)													
Travel history and contact history	x	x		x	х	x	х		x	х	x	x	х	x	x
Physical Examination c	x	x	x	20 65	x	x	x		x	х	x	x	х	x	x
Vital signs d	x	x	x	x	x	x	x	x	x	x	x	x	x	x	x
12-lead ECG	x														
Chest CT scan	x			08 80	58 80	98 130									
WOCBP serum pregnancy test e	x						x								
Clinical laboratory tests (urine routine) f	x			x	х				x						
Clinical laboratory tests (blood routine, blood chemistry) g	x			x	х				x						
Clinical laboratory tests (thyroid function) h	x			x					x					x	
Clinical laboratory tests (coagulation function) i	x			x					x						

Procedure/Assessm ent	Visit 0	Visit 1 Before prime vaccination	Visit 1 Prime vaccination & after vaccination	Visit 2	Visit 3 7 days after prime vaccination	Visit 4 14 days after prime vaccination		Visit 5 Boost vaccination & after vaccination	vaccination	after boost	Visit 8 21 days after boost vaccination	Visit 9 28 days after boost vaccination	Visit 10	Visit 11	Visit 12
Time Points	Screening D -14~D 0	Day 1	Day 1	24 h (±2 h)	Day 8 (±1 d)	Day 15 (±1 d)	Day 22 (±2 d)	Day 22 (±2 d)	Day 29 (±3 d)	Day 36 (±3 d)	Day 43 (±4 d)	Day 50 (±4 d)	Month 3 (D 85 ±7d)	Month 6 (D 184 ±9d)	Month 12 (D 366 ±9d)
HIV test (fingertip blood)	x														
SARS-CoV-2 testing j	x														
Treatment Randomization k		x	80												
Immunization 			X					x							
Collect blood samples for IgG antibody		х			34 30		х		х		x			х	х
Collect blood samples for neutralizing antibody		x					х		x		x			x	х
Collect blood samples for CMI test m		х							х						
Issue subject diaries n			x		х	х		х	х	х	х				
Collect subject diaries		9		х	x	x	x		х	х	х	x			
Record AEs since last visit	x	x	x	x	x	x	x	x	x	x	x	x	x	x	х
Local reaction assessment o			х	x	х	x	x	x	x	х	х	x			
Record concomitant medications/ products/ vaccinations		x	x	x	x	x	x	x	x	x	x	х	х	x	x

Procedure/Assessm ent	Visit 0	vaccination	Visit 1 Prime vaccination & after vaccination	Visit 2	Visit 3 7 days after prime vaccination	after prime		Visit 5 Boost vaccination & after vaccination	vaccination			Visit 9 28 days after boost vaccination		Visit 11	Visit 12
Time Points	Screening D -14~D 0	Company of Control	Day 1	24 h (±2 h)	Day 8 (±1 d)	Day 15 (±1 d)	Day 22 (±2 d)	Day 22 (±2 d)	Day 29 (±3 d)	Day 36 (±3 d)	Day 43 (±4 d)	Day 50 (±4 d)	Month 3 (D 85 ±7d)	Month 6 (D 184 ±9d)	Month 12 (D 366 ±9d)
Ask about the health condition of subject	х	x	x	x	х	x	x	x	x	x	x	x	x	x	х

- a Demographic information, to be obtained at Screening Visit, will include age (date of birth), sex, race, and ethnicity as provided by the subject.
- Medical history (incl. smoke and alcohol intake) will be collected at Screening Visit and at Visit 1 (Day 1) and will include any medical history that may be relevant to subject eligibility for trial participation such as prior vaccinations, concomitant medications, and previous and ongoing illnesses or injuries. Relevant medical history can also include any medical history that contributes to the understanding of an AE that occurs during trial participation, if it represents an exacerbation of an underlying disease/preexisting problem. Adverse occurrences before the prime vaccination of investigational vaccine/placebo are considered medical history.
- Complete physical examination (including height and weight) will be performed at Screening Visit. All subsequent are brief (symptom-directed) physical examinations, performed if deemed necessary or indicated by review of the subject's medical history, should assess clinically significant changes from the baseline examination. The findings should be documented in the subject's source document and transcribed into the electronic Case Report Form (eCRF). For any procedures at the site, the investigator shall follow his/her standard practice.
- Vital signs will performed at each on site visit, and at 1, 3, and 6 h (±15 min) post each immunization. Vital signs include systolic/diastolic blood pressure, pulse rate, respiratory rate, and body temperature.
- e In WOCBP women only: collect blood sample for testing β-hCG.
- Urine analysis: glucose, bilirubin, ketone, specific gravity, blood, pH, protein, urobilinogen, nitrite, and leukocytes. Microscopic urinalysis (based on dipstick results): urine sediment will be microscopically examined for the presence of red blood cells, white blood cells, casts, crystals, epithelial cells, and bacteria.
- g Clinical laboratory: (Chemistry) alkaline phosphatase, creatinine, ferritin, C-reactive protein, albumin, alanine aminotransferase, amylase, aspartate aminotransferase, gamma glutamyl transpeptidase, total bilirubin, blood urea, fasting blood sugar, lipase, sodium, potassium, calcium; (Hematology) hemoglobin, hematocrit, red blood cell count, white blood cell count and differential (neutrophils, lymphocytes, monocytes, eosinophils, basophils), platelet count.
- h Clinical laboratory tests (thyroid function): triiodothyronine (T3), thyroxine (T4), thyroid stimulating hormone.
-  Clinical laboratory tests (coagulation function): prothrombin time (PT), activated partial thromboplastin time (APTT), thrombin time (TT)), fibrinogen (FIB).
- j SARS-CoV-2 testing, including RT-PCR test of nasopharyngeal swabs and SARS-CoV-2 antibodies screening (fingertip blood). See Appendix C for procedures of collecting and handling specimens of nasopharyngeal swabs.
- Eligible virus naïve subjects with normal chest CT image enrolled at Screening will enter each cohort, and will be randomized to vaccination of BNT162b1 or placebo at Visit 1, within 7 days after Screening Visit 0.

- Each randomized subject will receive two doses of either BNT162b1 (10 or 30 μg) or placebo intramuscularly (IM) one vaccination each at Visit 1 (on Day 1) and at Visit 5 (on Day 22), conduct injections at one third of the deltoid muscle (preferably in the non-dominant arm).
- Each subject will receive diary cards to collect solicited reactions for 14 days after each vaccination (including the days of vaccine/placebo vaccination), and unsolicited AEs for 21 days after prime vaccination and 28 days after boost vaccination (including the days of vaccine/placebo vaccination).
- o From the beginning of prime vaccination to 28 days after boost vaccination, local reaction assessment should be conducted at 1, 3 and 6 h (±15 min) after each vaccination and at each site visit after vaccination.

